### **8.2.9. Other Analyses: Patient Reported Outcomes: FSFI**

Sexual function measured by the FSFI scale. It will be used an algorithm for determining domain scores and a composite full-scale score. The individual domain scores and full scale score of the FSFI are derived by a computational formula outlined in the SAP. Individual domain scores are obtained by adding the scores of the individual items that comprise the domain and multiplying the sum by the domain factor. The full scale score is obtained by adding the six domain scores. It should be noted that within the individual domains, a domain score of zero indicates that no sexual activity was reported during the previous evaluation.

### **8.2.10. Interim Analysis**

There will be an interim analysis after the first 10 included patients have completed 3 weeks of therapy. These patients will be evaluated after 3 weeks according to the study scheme.

Only safety data and the analytical values of FSH of these 10 firsts patients will be reviewed. It is expected that no significant changes from the postmenopausal to the premenopausal range in any patient.

The 10 patients included in the interim analysis will not be included in the final analysis, as they will not complete 4 months of therapy. For that reason, it will not be necessary to perform a correction of the final alpha.

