#### **1.4 Management of sexual adverse effects derived from the treatment of breast cancer patients**

Taking into consideration that many women diagnosed with breast cancer today will be long-term survivors of their disease, the long-term impact of therapy on their well-being and specifically on their sexual adverse effects has become a growing topic for research (9).

In order to overcome symptoms of estrogen deprivation, vaginal moisturizers or, sometimes, low dose topical estrogens are used in daily clinical practice, despite the inexistence of adequate clinical trials that support their use. Non-hormone vaginal moisturizers relieve urogenital symptoms, however their efficacy is significantly lower compared to vaginal estrogens (10). In contrast to oral hormone therapy, some consider that local application of estrogens seems to be safe in postmenopausal breast cancer patients (11). However, the report of a small prospective observation (12) advised caution with the use of vaginal estradiol in breast cancer patients receiving aromatase inhibitors, as an increase of serum estradiol levels was found that potentially could counteract endocrine breast cancer treatment (13).

A study using lower doses of estradiol presented in the 2013 ASCO Annual Meeting showed no changes in FSH while sporadic elevations of estradiol were seen in 5 out of 26 studied patients. The significance of this is difficult to judge as the full results have not been published yet (14).

According to the publication “*Practical guidelines for managing menopausal symptoms after breast cancer*”, the use of vaginal estradiol in patients treated with aromatase inhibitors was discouraged, but there was recommended the application of vaginal estriol, a much less potent estrogen than estradiol, in case estrogen therapy were deemed necessary (15).

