### 3.1.1 Early Safety Review

There will be an initial safety phase of the study, in which 10 patients will be included (also randomized 4:1) to obtain some preliminary safety data and FSH values prior to the recruitment of the rest of the group under study.

These women will receive the study treatment over 3 weeks (8 will receive estriol vaginal gel and 2 placebo moisturizing gel). FSH levels in serum will be analysed at screening, baseline and at week 3 (day 22 +/- 3 days). An independent data monitoring committee (IDMC) will review the results (together with safety data) which will advise the chief investigators about a go /no-go decision with the other 60 patients to complete the study. The study will continue if no significant changes in FSH levels from postmenopausal to premenopausal levels are observed.

These 10 patients will be recruited in two sites in Spain, 5 patients in each one. These patients will have estrogens, and FSH and LH determined at screening, baseline and at week 3.

**Figura 2:** Study Design of the Initial Safety Phase

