## **8.3 Data Monitoring Committee**

The study will use an IDMC. The IDMC membership and governance is outlined in a separate charter.

The IDMC will be responsible to review the FSH and safety data from the first 10 patients included in the study and to advise the sponsor and chief investigator about a go /no-go decision with the other 60 patients to complete the calculated sample size.

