m	Two smears (with two different spatulas provided by the sponsor one to take the sample and the other to take the countersample) will be made per patient for each sample (sample and countersample), which will be obtained from the bottom of the right and left vaginal sac respectively. Each smear will be suitably labelled with the corresponding labels provided to the investigator. The vaginal smears will be fixed whilst they are still moist with a water-soluble fixation spray for cytodiagnosis. The cytologic samples will be sent to central laboratory (full instructions will be given in the Laboratory Manual).
n	FSFI: Female Sexual Function Index questionnaire; patients must preferably complete these instruments in the hospital and prior to having any tests and to any discussion of their progress with healthcare personnel at the site. Interviewer administration in clinic may be used under special circumstances (eg, patient forgot their glasses or feels too ill).

ñ	
Dosage schedule:
 
Weeks 1-3: single daily application
 
Weeks 4-12: twice weekly administration.
 
The treatment will be administered for 12 weeks.
 
The Principal Investigator, Sub-Investigator, study nurse or the Gynecologist must explain to the patient how to administer the vaginal gel. It is advised that the first application consider be performed in presence of the gynecologist or oncologist.
 
Women will be instructed to administer the gel themselves for the rest of applications.
 
The 10 patients included in the safety phase to obtain some preliminary safety data and FSH values prior to the recruitment of the rest of the group under study. These women will receive the study treatment over 3 weeks. These 10 patients will only perform the determinations of all hormone (FSH, LH, estriol, estradiol and estrone)

o	
The baseline visit may be performed in two consecutive days (no more), although it will be best performed it in one day. Treatment administration will always be the last of the baseline visit procedures.

p	
These tests should be performed after the definite inclusion of the patient in the study, as part of the baseline visit.

---

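### The go/no-go review of the 10 lead-in women is limited to FSH and safety data, so the estrogen and LH results measured in the same women do not reach the IDMC before 60 more are enrolled

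*Protocol*

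**What the plan says.** The lead-in phase (Protocol 3.1.1) randomizes 10 women: "8 will receive estriol vaginal gel and 2 placebo moisturizing gel". They are treated for 3 weeks, and the IDMC then advises whether to proceed with the other 60.

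**Data reviewed.** Section 8.2.10: "Only safety data and the analytical values of FSH of these 10 firsts patients will be reviewed". Section 8.3: "The IDMC will be responsible to review the FSH and safety data from the first 10 patients included in the study". Both name FSH separately from safety data, and neither names another hormone.

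**Continuation rule.** Section 3.1.1: "The study will continue if no significant changes in FSH levels from postmenopausal to premenopausal levels are observed". Section 8.2.10 words it per patient: "It is expected that no significant changes from the postmenopausal to the premenopausal range in any patient". Neither section gives a number for premenopausal.

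**Data collected.** Section 3.1.1: "These patients will have estrogens, and FSH and LH determined at screening, baseline and at week 3". A footnote to the Study Schedule (Attachment 1) lists the analytes: "These 10 patients will only perform the determinations of all hormone (FSH, LH, estriol, estradiol and estrone".

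**Hypothesis and later use.** Section 1.6 states a hypothesis with two parts: no significant gonadotropin decline and no increase in systemic estrogens. Section 8.2.10 leaves these 10 women out of the final analysis.

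**The concern.** The gate covers part of what the trial sets out to show. The estrogen half of the hypothesis, and LH from the gonadotropin half, are measured at week 3, which is the end of the daily-application phase. The documents keep these results out of the one decision they could inform. Because the women are also left out of the final analysis, the protocol names no review or analysis that would use their estrogen and LH values.

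The background section shows that FSH and estrogens need not move together. Section 1.4 describes a vaginal estradiol study that "showed no changes in FSH while sporadic elevations of estradiol were seen in 5 out of 26 studied patients".

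At stake is whether 60 further women with hormone receptor-positive cancer, on treatment meant to deprive the tumor of estrogen, are enrolled without the committee having seen estrogen results that already exist.

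**Working it through.** **1. Which findings would reach the IDMC?**

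| Week-3 finding in a lead-in woman | Measured? | Shown to the IDMC? | Covered by the continuation sentence? |
|---|---|---|---|
| FSH falls to the premenopausal range | yes | yes | yes |
| FSH falls but stays postmenopausal | yes | yes | no |
| LH changes, FSH does not | yes | no | no |
| Estriol, estradiol or estrone rises, FSH does not change | yes | no | no |

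Rows three and four are the gap in the data shown. Row two is a gap in the stated rule only.

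**2. The plan's own FSH figure.** Section 8.1 plans on a fall from 75.7 to 66.0, which is 9.7 mIU/ml (9.7/75.7 = 12.8%), with SD 22.3. A paired t-test at two-sided 0.05 has power 0.805 at n = 44 and 0.796 at n = 43, so the stated 44 is reproduced. The go/no-go rule has no such calculation behind it.

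**3. Illustration for row four.** Assume the cited rate, 5/26 = 19.2%, applied to the 8 estriol women:

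- P(at least one elevation) = 1 − (21/26)^8 = 0.82.
- The exact 95% interval for 5/26 is 6.6% to 39.4%. This gives 1 − (1 − 0.066)^8 = 0.42 and 1 − (1 − 0.394)^8 = 0.98.

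In that pattern FSH is unchanged, so a review of FSH alone gives no signal.

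**4. How the FSH crossing rule behaves.** The protocol gives no premenopausal limit. Its only FSH threshold is 40 mIU/ml, in one branch of inclusion criterion 4. I take 40 as an assumed border and 20 to 25 as alternatives.

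- A woman at the planning mean must fall 75.7 − 40 = 35.7 (47%) to cross 40. A woman at the bottom of the cited range must fall only 45.6 − 40 = 5.6.
- Simulation: 8 women, baseline normal with mean 75.7 and SD 22.3, week-3 SD the same, and correlation between the two values assumed to be 0.5 to 0.9. Go means that no woman moves from at or above the cut to below it.

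| Assumed cut (mIU/ml) | Go, true mean fall of 9.7 | Go, no effect |
|---|---|---|
| 40 | 44–55% | 72–85% |
| 20–25 | 78–89% | 92–98% |

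At 40 the rule is noisy: it fires in 15–28% of lead-ins with no effect and misses about half of those with the planned fall. At 20 to 25 it seldom fires in either case.

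**The case against.** **FSH is a reasoned choice.** It is the primary endpoint. The only data in the protocol on vaginal estriol with an aromatase inhibitor (section 1.4, at 0.5 mg) show FSH and LH falling with no detected estrogen rise. For the 50 µg gel, section 1.5 reports negligible plasma estriol and unchanged FSH and LH in healthy women. This stands as a reason for including FSH. It is weaker as a reason for excluding the rest, because section 1.4 itself says that the earlier estriol study's assay lacked sensitivity, and section 6.2 brings in an ultrasensitive assay for that purpose.

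**The 5 in 26 comes from another drug.** It was seen with vaginal estradiol, the protocol does not define elevation, and it calls the significance hard to judge. This stands: the 82% is not a forecast for this gel.

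**The review is not blind.** A reader might infer that any sign of systemic absorption would be hidden from the IDMC. The documents do not support that. The IDMC receives the FSH values themselves and its role is advisory, so it could comment on a decline within the postmenopausal range. A reader might also infer from the 47% that the rule could hardly ever fire. That figure holds only for a woman at the mean and for an assumed border, and the simulation at 40 shows frequent crossings.

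**The charter is separate and not shown.** It may say more. A charter that added estrogens would, however, contradict the restriction in section 8.2.10.

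**There is a practical reason for an FSH gate.** Section 3.2 gives a 2–3 week wait for FSH results, and the estrogens go to a second laboratory. This is a real cost, taken up in the fix.

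**Conclusion.** The point holds in a limited form. Sections 3.1.1, 8.2.10 and 8.3 consistently confine the go/no-go review to FSH and safety data, while the hypothesis and the sampling schedule reach further. An estrogen or LH change without an FSH change would not be seen before the main phase opens. An FSH decline that stays postmenopausal would be seen, but the continuation sentence does not address it.

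This conclusion rests on the text alone and needs no assumption. The sizes do need assumptions: 82% (42–98%) requires that an estradiol-product rate carry over to this gel, and the crossing probabilities require an assumed border, normality and an assumed correlation. They show that the omission could matter, not how likely it is.

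The primary analysis is unaffected, because these 10 women are not in it. This is an inexpensive improvement in patient protection, not an error in the trial's inference.

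**What to change.** 1. In sections 8.2.10 and 8.3, replace the restriction with: safety data plus individual FSH, LH, estriol, estradiol and estrone values at every lead-in time point at which each is collected.
2. List each woman's FSH change from the mean of her screening and baseline values to week 3. Section 8.2.6 already uses that pair of values for intra-individual variation.
3. Change section 3.1.1 at the same time. Its FSH-only continuation sentence must be reconciled with the two-part hypothesis in section 1.6, so that the added hormones have a stated role in the advice. The threshold or stopping rule is for the sponsor and the IDMC to set; none is proposed here.
4. Reconcile section 3.1.1, which has estrogens determined at screening, with section 6.2 and the Study Schedule, which start estrogen sampling at baseline.
5. Do not ask for an arm mean with a 95% interval in the placebo group: with 2 women there is 1 degree of freedom and a t multiplier of 12.7. If listings by arm are wanted, give them to the IDMC only, by a stated unblinded route consistent with section 5.8, which now releases the codes to the project statistician only after the study is finalized.

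Cost: no new samples and a few more listings. The LC-MS/MS results from the second laboratory may extend the 2–3 week wait stated for FSH, so section 3.2 should give the turnaround for both laboratories.

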## **8.3 Data Monitoring Committee**

The study will use an IDMC. The IDMC membership and governance is outlined in a separate charter.

The IDMC will be responsible to review the FSH and safety data from the first 10 patients included in the study and to advise the sponsor and chief investigator about a go /no-go decision with the other 60 patients to complete the calculated sample size.

## **8.4 Criteria for End of Study**

This study will be considered complete following the data cut-off date and datalock for the final analysis. The data cut-off date for the final analysis will occur after all enrolled patients have completed the safety visit 30 (+/-5) days after the last study drug administration.

---

## **9. Informed Consent, Confidentiality, Responsibility Insurance and Regulatory Considerations**

### **9.1. Informed Consent**

The investigator is responsible for ensuring that the patient understands the risks and benefits of participating in the study, including answering any questions the patient may have throughout the study and sharing any new information that may be relevant to the patient's willingness to continue her participation in the trial in a timely manner.

The informed consent document will be used to explain the risks and benefits of study participation to the patient in simple terms before the patient is entered into the study, and to document that the patient is satisfied with her understanding of the risks and benefits of participating in the study and desires to participate in the study.

The investigator is responsible for ensuring that informed consent is given by each patient or legal representative. This includes obtaining the appropriate signatures and dates on the informed consent document prior to the performance of any protocol procedures and prior to the administration of study treatment.

As used in this protocol, the term "informed consent" includes all consent and assent given by patients or their legal representatives.

If new safety information results in significant changes in the risk/benefit assessment, the consent form should be reviewed and updated if necessary. All patients (including those already being treated) should be informed of the new information, given a copy of the revised form and give their consent to continue in the study.

### **9.2. Respect of Confidentiality**

The investigator will be responsible for preserving the suitable information about each patient (for example, name, address, telephone number, social security number and study identification) so that the competent authorities can have access to said information if necessary. These records must be confidentially preserved for the time indicated by the legislation.

The investigators and the sponsor will maintain the confidentiality of all patients participating in the study, according to Good Clinical Practice, GCP and local legislation.

### **9.3. Responsibility Insurance**

The Sponsor has signed an insurance policy to cover the responsibilities of the investigator and those of other parties participating in the study.

### **9.4. Regulatory Considerations**

This study will be conducted in accordance with the ethical principles that have their origin in the Declaration of Helsinki and that are consistent with good clinical practices and the applicable laws and regulations. The investigator, head of the medical institution, or designee will promptly submit the protocol to applicable ethical review board(s).

#### **9.4.1 Investigator Information**

Physicians with a specialty in medical oncology and gynecology will participate as investigators in this clinical trial.

If investigators are added after the study has been approved by the sponsor, an ERB/IRB, or a regulatory agency, these additions will not be considered changes to the protocol.

#### **9.4.2 Protocol Signatures**

After reading the protocol, each principal investigator will sign the protocol signature page and send a copy of the signed page to Sponsor.

---

## 10. Practical Considerations

### 10.1. Monitoring, Audit and Inspections

The study will be monitored by means of regular visits of the patients. During the visits to the center, the monitor must review the original records of the patients, the records of medication stocks and document preservation. The monitor must also evaluate the study procedures and discuss the possible problems with the investigator. During the course of the study, audit visits can be carried out in the participating centers. The investigator will allow direct access to the source documents/data for the tasks of monitoring, audit, reviewed by the ERB and the inspection by the Competent Authorities.

### 10.2. Preservation of Study Documentation

The copies of all the relevant information will be preserved by the investigator for a period of at least 5 years after the end of the study, according to current legislation.

### 10.3. Protocol Modification

Once it has been authorized by the ERB and the competent authority any protocol modification must be documented by writing, in the form of an amendment.

The amendments must be duly identified, by its chronological order number, dated and signed by the sponsor and the chief investigator.

All the protocol amendments must be notified to the ERBs involved in the trial and to the competent authority. If the modifications are relevant, the authorization of the involved ERBs and/or the competent authority will be necessary before their application.

After reading the protocol amendment, each principal investigator will sign the protocol amendment signature page and send a copy of the signed page to Sponsor.

### 10.4. Use of the Information and Publication

All the information concerning the study treatment provided by the sponsor in relation to this study, and not previously published, is considered to be confidential information with property right of the sponsor. This information comprises the basic information about the product, the clinical protocol, the work forms where appropriate, the e-CRFs, the assessment methods, the technical methodology and the basic scientific data. This confidential information will be the property of the sponsor, it must not be disclosed to third parties without the prior written consent of the sponsor and it must not be used other than for the purposes of the study.

The information developed during the practice of this clinical study is also considered to be confidential. This information can be disclosed to the extent considered necessary by the sponsor.

To allow the use of the information derived from this study and to ensure the compliance with the current rules, the investigator is obliged to provide GEICAM (on behalf of the sponsor) with all the results of examinations and all the data developed in this study. Except in that required by law, the information obtained during the study can only be provided to the doctors and to the

competent authorities by the Sponsor or delegated people on behalf of the sponsor. The sponsor commits to publish the results of the study and to present them in scientific meetings either if they are positive or negative.

#### **10.5. Ethics Committees**

The protocol and the informed consent document will be reviewed by the involved ERBs. The single decision of the ERBs referring to the development of the study will be provided in writing to GEICAM (on behalf of the sponsor).

GEICAM (on behalf of the sponsor) will submit the required reports of the progress of the study to the ERB and will communicate the possible SAE, the life-threatening adverse events and deaths. At the end of the study, GEICAM (on behalf of the sponsor) will inform the ERB of trial closure.

---

### Protocol Attachment 1. Study Schedule

Study Schedule of Events and Timelines. ITFE-2026-C10 (BLISSAFE Study)	During Study Treatment. All visits (except week 1) +/- 3 days of scheduled treatment day.	Post-treatment (4 weeks) from the last study drug dose
---	--	---

Visits	Screening	Baseline	Week 1	Week 3	Week 8	Week 12 or early withdrawal visit	Post-treatment (4 weeks) from last study drug dose	
Day	Within 14 days prior to the registration	1 o	8 (+/- 2 days)	22 (+/-3d)	57 (+/-3d)	85 (+/- 3d)	+30 (+/-5d)	
Procedure/Laboratory/ Diagnostic Test								
ICD for Entry (before any study specific tests) a	X							
Medical and surgical history and demographics b	X							
Physical examination c	X		X	X	X	X	X	
ECOG PS	X		X	X	X	X	X	
Hematology d	X					X	X	
Blood Chemistry e	X					X	X	
Urine Test f	X					X	X	
Endometrium by transvaginal ultrasound g	X					X		
Moderate or severe vaginal dryness	X							
Review Inclusion/Exclusion Criteria	X	X						
Concomitant medications	X	X	X					

Visits	Screening	Baseline	Week 1	Week 3	Week 8	Week 12 or early withdrawal visit	Post-treatment (4 weeks) from last study drug dose
Day	Within 14 days prior to the registration	1 o	8 (+/- 2 days)	22 (+/-3d)	57 (+/-3d)	85 (+/- 5d)	+30 (+/-5d)
AEs and SAEs h	X	X	X				
Blood (serum) samples for FSH and LH determination i	X	X p	X	X	X	X	
REGISTRATION / RANDOMIZATION		X					
Blood (plasma-EDTA) samples for estriol, estradiol and estrone determination i		X p	X	X	X	X	
Gynaecological examination j		X p		X		X	
Symptoms and signs of vaginal atrophy k		X p		X		X	
Measurement vaginal pH l		X p		X		X	
Vaginal cytology sample to evaluate the vaginal Maturation Value m		X p		X		X	
FSFI questionnaire n		X p		X		X	
Study drug/ placebo dosing n		X n	X n				

